#### **6.5.1.3 Derivation of CDC Case Definition of COVID-19**

This is a secondary efficacy endpoint: the incidence of the first occurrence of cases (CDC Case Definition of COVID-19) starting 14 days after the first dose of IP, and cases starting 14 days after the second dose of IP. CDC Case Definition of COVID-19 is defined as symptomatic disease based on the criteria specified in the table listed below. Cases are defined as participants meeting clinical criteria based on both symptoms for COVID-19 and positive RT-PCR test results.

While Part 2 is still blinded for any age group, surveillance for COVID-19 symptoms will be conducted via biweekly telephone calls or eDiary. Subjects reporting CDC Case Definition of COVID-19 symptoms, as defined in Section 7.3.2 of the protocol, will be arranged an illness visit to collect a nasal swab for SARS-CoV-2.

For this efficacy endpoint, a CDC Case Definition of COVID-19 case will be identified as a positive post-baseline RT-PCR test result that is prompted by symptom(s), together with eligible symptoms, i.e. a positive PCR result of the eligible symptoms summarized below in Table 4.

**Table 4. Derivation for CDC Case Definition of COVID-19**

|                           | COVID-19   |
|---------------------------|---|
| Post-baseline PCR results | Positive, AND  |
| Systemic Symptoms         | at least ONE of the following systemic symptoms: Fever (temperature $\geq 38^{\circ}\text{C}/\geq 100.4^{\circ}\text{F}$ ) or chills (of any duration, |

|                      |   |
|----------------------|---|
|                      | including $\leq$ 48 hours), fatigue, headache, myalgia, nasal congestion or rhinorrhea, new loss of taste or smell, sore throat, abdominal pain, diarrhea, nausea/vomiting, poor appetite/poor feeding; OR            |
| Respiratory symptoms | at least ONE of the following respiratory signs/symptoms: cough (of any duration, including $\leq$ 48 hours), shortness of breath or difficulty breathing (of any duration, including $\leq$ 48 hours). |

The date of documented CDC Case Definition of COVID-19 (case) will be the later date of ([1 systemic symptom reported, or respiratory symptom reported] and, [date of positive PCR test]). Specifically, the date of documented CDC Case Definition of COVID-19 will be the later date of the following two dates (date of positive PCR test, and the date of eligible symptom(s)), and the two dates should be within 14 days of each other.

- Date of positive PCR test,
- Date of eligible symptom(s), defined as earliest of
  - Respiratory symptom: earliest date of an eligible respiratory symptom is reported
  - Systemic symptoms: earliest date of the eligible systemic symptom is reported

The time to the first occurrence of CDC Case Definition of COVID-19 will be calculated as:

Time to the 1st occurrence of CDC Case Definition of COVID-19 = Date of documented CDC Case Definition of COVID-19 – Date of randomization + 1. (For Part 1, switch date of randomization to date of first injection).

Cases will be counted start 14 days after the 2nd injection, i.e. date of documented CDC Case Definition of COVID-19 - Date of the 2nd injection  $\geq$  14.

#### **6.5.1.4 Derivation of COVID-19 (P301 Primary Definition)**

This is a secondary efficacy endpoint: the incidence of the first occurrence of COVID-19 cases meeting the P301 primary definition, starting 14 days after the first dose of IP, and COVID-19 cases starting 14 days after the second dose of IP.

The P301 primary definition of COVID-19 is defined by the following criteria:

- At least TWO of the following systemic symptoms: Fever ( $\geq 38^{\circ}\text{C}/\geq 100.4^{\circ}\text{F}$ ), chills, myalgia, headache, sore throat, new olfactory and taste disorder(s), OR
- The participant must have experienced at least ONE of the following respiratory signs/symptoms: cough, shortness of breath or difficulty breathing, OR clinical or radiographical evidence of pneumonia; AND
- At least one positive RT-PCR test for SARS CoV-2

Date of the documented definition of COVID-19 (P301 Primary Definition) will be later date of:

- Date of the positive RT-PCR test (prompt by symptom)
- Date of eligible symptom(s), defined as earliest of
  - Respiratory symptom: earliest date of an eligible respiratory symptom is reported
  - Systemic symptoms: earliest date of the eligible systemic symptoms are reported.

and the two dates should be within 14 days of each other.

COVID-19 (P301 Primary Definition) cases will also be summarized based on tests performed after randomization (For Part 1, switch date of randomization to date of first injection).

### **6.5.2. Analysis Method**

The number and percentage of subjects who had an event (i.e. the first asymptomatic SARS-CoV-2 infection) will be summarized in the PP set for Efficacy.

The incidence rate will be provided by age and vaccination group, calculated as the number of cases divided by the total person-time. The 95% CI of the incidence rate will be calculated using the exact method (Poisson distribution) and adjusted by person-time.

Person-time is defined in Part 2 as the total time from randomization date to the date of event, last date of study participation, censoring time, or efficacy data cutoff date, whichever is earlier. For Part 1, switch randomization date to date of first injection.

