### 3.2. Secondary Endpoints

The secondary objective will be evaluated by the following endpoints:

- The GM values of SARS-CoV-2 S protein-specific bAb on Day 1, Day 57 (1 month after Dose 2), Day 209 (6 months after Dose 2), Day 394 (1 year after Dose 2), BD-Day 1 (at least 3 months or 6 months after Dose 2), BD-Day 29 (1 month after mRNA-1273 booster dose or third dose), BD-Day 181 (6 months after mRNA-1273 booster dose or third dose), and BD-Day 366 (1 year after mRNA-1273 booster dose or third dose).
- The GM values of SARS-CoV-2-specific nAb on Day 1, Day 57 (1 month after Dose 2), Day 209 (6 months after Dose 2), Day 394 (1 year after Dose 2), BD-Day 1 (at least 3 months or 6 months after Dose 2), BD-Day 29 (1 month after mRNA-1273 booster dose or third dose), BD-Day 181 (6 months after mRNA-1273 booster dose or third dose), and BD-Day 366 (1 year after mRNA-1273 booster dose or third dose).
- The incidence of SARS-CoV-2 infection including symptomatic and asymptomatic infection (by serology and/or RT-PCR), starting 14 days after the second dose of IP, and starting 14 days after the first dose of IP. SARS-CoV-2 infection will be defined in participants with negative SARS-CoV-2 at baseline:
  - bAb level against SARS-CoV-2 nucleocapsid protein negative at Day 1 that becomes positive (as measured by Roche Elecsys) post baseline, OR
  - Positive RT-PCR post baseline.
- The incidence of SARS-CoV-2 infection measured by RT-PCR and/or bAb levels against SARS-CoV-2 nucleocapsid protein (by Roche Elecsys) post baseline in participants with negative SARS-CoV-2 at baseline, in the absence of any COVID19 symptoms, starting 14 days after the second dose of IP, and starting 14 days after the first dose of IP

- The incidence of the first occurrence of CDC Case Definition of COVID-19 post baseline, starting 14 days after the second dose of IP, and starting 14 days after the first dose of IP. COVID-19 is defined as symptomatic disease based on the following criteria according to CDC case definition:
  - The participant must have a positive test for SARS-CoV-2 by RT-PCR; AND
  - Either

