#### **4.3. Randomization**

Random assignment of participants in Part 2 of the study will use a centralized interactive response technology, in accordance with pregenerated randomization schedules. Up to 4,000 participants each in the 6 years to < 12 years, 2 years to < 6 years, and 6 months to < 2 years age groups will be randomized in a 3:1 ratio to the mRNA-1273 arm (n = up to 3,000 participants in each group) or placebo arm (n = up to 1,000 participants in each group).

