**Table 2: Phlebotomy Schedule for Serology, Biomarker Sample, and CMI for Part 2 (Expansion) of the Study**

**For participants that chose to receive a booster dose under protocol Amendment 7, please see separate SAP for part 2 open-label phase and booster doses's section 8.7 appendix G for the booster dose phlebotomy schedule.**

**If Day 209/Day 394 blood draw is within 30 days of planned BD-Day 1, BD-Day 1 blood draw can be used for Day 209/Day 394.**

| Cohort  | Number of Subjects                    | Study Visit Day   |                  |                          |     |     |                                    |                                    |
|---|---------------------------------------|-------------------|------------------|--------------------------|-----|-----|------------------------------------|------------------------------------|
|   |                                       | D1  | D29  | D30
(+3)  | D43 | D57 | D209
(+30
days)  | D394
(+30
days)  |
| Phlebotomy Schedule for Serology: To be Executed Within Age Group  |                                       |                   |                  |                          |     |     |                                    |                                    |
| A   | First 176 (132 mRNA-1273: 44 placebo) | X                 | X                |                          |     | X   |                                    |                                    |
| B   | Next 176 (132 mRNA-1273: 44 placebo)  | X                 |                  |                          |     | X   | X                                  |                                    |
| C   | Next 176 (132 mRNA-1273: 44 placebo)  | X                 |                  |                          |     | X   |                                    | X                                  |
| D   | Remainder of the age group            | X                 |                  | X            |     |     |                                    |                                    |
| Phlebotomy Schedule for Cell-Mediated Immunity: To be Executed Within Each Age Group at Selected VTEU Sites only |                                       |                   |                  |                          |     |     |                                    |                                    |

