| E (CMI with exploratory serology)   | 24 (18 mRNA-1273: 6 placebo)          | X                 |                  |                          | X   |     | X                                  | X                                  |

Abbreviations: CMI = cell-mediated immunity; D = day; VTEU = Vaccine and Treatment Evaluation Units.

1. On Day 1, sample must be collected prior to randomization and dosing. On Day 29, sample must be collected prior to dosing.
2. If a Day 1 (baseline) blood sample cannot be obtained in either Part 1 or Part 2, the participant will be considered either a screen failure due to inability to satisfy inclusion criterion 3 or could be scheduled for rescreening. Participants may be rescreened 1 time, either within same screening period for Part 1 or Part 2 or in a new screening period for Part 2 if the initial screening was in Part 1. If the participant is rescreened and a blood sample still cannot be obtained, then he/she will be considered a screen failure due to inability to satisfy inclusion criterion 3.
3. Serum sample from ~4 ml of blood only, to be stored for potential future use for biomarker assessment
4. If the participant decides to receive a booster dose, the BD1 blood draw (Protocol Table 15) can be used for Day 209 or Day 394 (Protocol Table 14).

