18. For Part 1, only the first approximately 75 participants in Arm 1 and Arm 2 will have postbaseline scheduled blood draws; the 300 participants in each of the expansion part of Arm 1 and Arm 2 may have an optional blood draw on Day 57. All participants in Arm 3, 4, 5, 6 and 7 will have postbaseline blood draws on Day 57, Day 209 and Day 394.

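### The serology-and/or-RT-PCR infection rates use the whole efficacy set as denominator, but most Part 2 children have no planned post-baseline nucleocapsid test, so each arm's rate mixes two ascertainment schemes and is understated

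*SAP*

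**What the plan says.** - **Endpoint.** Section 3.2 lists "The incidence of SARS-CoV-2 infection including symptomatic and asymptomatic infection (by serology and/or RT-PCR") as a secondary endpoint, with asymptomatic infection as a second one. Under sections 6.5.1.1 and 6.5.1.2, seroconversion alone or a positive RT-PCR alone is enough for a case.
- **Analysis set and person-time.** Section 6.5.2: "The number and percentage of subjects who had an event (i.e. the first asymptomatic SARS-CoV-2 infection) will be summarized in the PP set for Efficacy". Person-time in Part 2 runs from randomization to event, end of participation, censoring or cutoff. Section 6.5 makes mITT1 the primary set for counting from 14 days after dose 1. Sections 5.3, 5.8 and 5.9 require nucleocapsid serology at baseline only.
- **Who is tested.** Table 2 gives Cohort A as "First 176 (132 mRNA-1273: 44 placebo"), B and C as the same size, and E as 24 children at selected sites with exploratory serology. Cohort D is the "Remainder of the age group". Its Day 30 draw carries the footnote "Serum sample from ~4 ml of blood only, to be stored for potential future use for biomarker assessment". Section 6.4.1 gives Cohort D a Day 1 sample only.
- **Enrolment.** Section 4.3: "Up to 4,000 participants each in the 6 years to < 12 years" group and in each of the two younger groups, who "will be randomized in a 3:1 ratio to the mRNA-1273 arm" or placebo.
- **Swabs.** Appendix E schedules nasal swabs on Days 1, 29, 57, 209 and 394 with no restriction to those cohorts. Day 43 is added for the cohort at selected sites.
- **Part 1.** The last footnote of Appendix E: "only the first approximately 75 participants in Arm 1 and Arm 2 will have postbaseline scheduled blood draws". The 300 expansion children in each of those arms may have an optional Day 57 draw. Arms 3 to 7 have draws on Days 57, 209 and 394.

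**The concern.** A case definition with two routes needs both routes open to everyone in the denominator. Here most Part 2 children add person-time during which the serology route is closed. The resulting rate is neither an RT-PCR rate nor a serology-inclusive rate. It is a weighted mix whose weights depend on how many children were enrolled after Cohorts A to C filled.

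What is at stake is the meaning of two secondary endpoints. A reader would take a rate labelled as serology and/or RT-PCR to be the rate of all infection. Scheduled swabs are up to six months apart, so an infection without symptoms that clears between swabs can be recorded only by serology. That is the type of infection these endpoints exist to capture.

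Section 6.5.3 does not repair this. Its sensitivity analyses change the analysis set, the start of counting, baseline status and the type of test accepted for COVID-19. None separates the two components or restricts to children who are tested.

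**Working it through.** **1. Reproduce the plan's own figure.** Cohorts A + B + C = 3 × 176 = 528, split 3 × 132 = 396 to mRNA-1273 and 3 × 44 = 132 to placebo. Section 4.2 gives approximately 528 (~396 and ~132), an exact match.

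**2. Coverage by post-baseline serology.** Adding Cohort E (18 + 6 = 24): 528 + 24 = 552 per age group, split 414 to 138.

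| Enrolled per age group | Coverage = 552/N | Cohort D share |
|---|---|---|
| 4,000 (ceiling) | 13.8% | 86.2% |
| 3,000 | 18.4% | 81.6% |
| 2,000 | 27.6% | 72.4% |
| 1,500 | 36.8% | 63.2% |

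By arm at the ceiling, the Cohort D share is (3,000 − 414)/3,000 = 86.2% on vaccine and (1,000 − 138)/1,000 = 86.2% on placebo. Cohort A has no draw after Day 57, so beyond that visit only B, C and E remain: 376/4,000 = 9.4%. These are shares of enrolled children. They carry over to the PP Set and mITT1 Set if exclusions are similar across cohorts.

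**3. Does the stored Cohort D sample help?** Day 30 is one day after dose 2. Post-dose-2 counting starts 14 days after dose 2, about Day 43, so the sample falls too early. It would fall inside the post-dose-1 window, but no nucleocapsid test on it is planned.

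**4. Understatement in each arm.** Let s be the share of infections that swabs would miss and serology would find, and c the coverage. Taking serology as complete in the covered children, reported/true = (1 − s) + c·s, so the understatement is s × (1 − c). The SAP gives no value for s; the values below are assumptions.

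| s (assumed) | N = 4,000 (c = 0.138) | N = 1,500 (c = 0.368) |
|---|---|---|
| 0.1 | 8.6% | 6.3% |
| 0.3 | 25.9% | 19.0% |
| 0.5 | 43.1% | 31.6% |

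**5. Effect on an informal comparison of arms.** Assume N = 4,000, placebo risk 10% and s = 0.5 on placebo. The observed placebo risk is 10% × (0.5 + 0.5 × 0.138) = 5.69%.

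| Assumed effect on RT-PCR-detected / serology-only infections | True reduction | Observed vaccine risk | Observed reduction |
|---|---|---|---|
| 50% / 50% | 50% | 2.845% | 50% |
| 60% / 20% | 40% | 10% × (0.5 × 0.4 + 0.069 × 0.8) = 2.552% | 55% |
| 40% / 70% | 55% | 10% × (0.5 × 0.6 + 0.069 × 0.3) = 3.207% | 44% |

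Equal effects leave the ratio unbiased, although the risk difference shrinks from 5.0 to 2.8 percentage points. Unequal effects can bias the ratio either way.

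**The case against.** The strongest reply is that these are descriptive secondary rates. Section 6.5.2 gives counts, percentages and an incidence rate with an exact Poisson interval by group; it defines no efficacy estimate, rate ratio or test. Efficacy is inferred from immunogenicity. Every cohort is split 3:1, so testing is balanced between arms. Scheduled swabs cover Cohort D, and section 6.5.1.2 accepts a positive scheduled swab as an asymptomatic case. The sampling schedule is disclosed in the same SAP.

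Most of this stands, and it limits the point in four ways where a reader might infer more:

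- *That Cohort D children cannot become cases.* They can, by scheduled or illness-visit RT-PCR. The loss is partial, and its size depends on s.
- *That the vaccine-placebo effect is exaggerated.* No such effect measure is planned, the bias needs a difference in vaccine effect that the SAP does not assert, and it can run in either direction.
- *That 86% is a fixed figure.* It holds at 4,000, which is a ceiling. At lower enrolment the uncovered share falls.
- *That Part 1 has the same gap.* It is confined to the expansions of Arms 1 and 2, where a Day 57 draw is optional. Part 1 has no placebo arm.

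The reply does not remove the dilution of the absolute rates. Balance between arms does not make a rate mean what its label says, and disclosing the schedule in Table 2 does not tell a reader of the results table how many children could have been found by serology.

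**Conclusion.** The point holds for the absolute rates. In Part 2, the infection and asymptomatic-infection incidence in each arm mixes two ascertainment schemes, in the PP Set and in mITT1 alike. The all-infection rate is understated by s × (1 − coverage): at 4,000 per age group, about 9% to 43% for s between 0.1 and 0.5; at 1,500, about 6% to 32%. The range of s is assumed, and the formula takes serology as complete in all 552 children. That is generous, because Cohort A stops at Day 57 and the SAP does not say that Cohort E is tested for nucleocapsid.

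No directional bias in a vaccine-placebo contrast can be claimed from the document. The matter concerns secondary, descriptive endpoints. It deserves correction because existing data allow it and because the rates cannot otherwise be read as labelled.

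**What to change.** In sections 6.5.2 and 6.5.3, for both the PP Set for Efficacy and mITT1:

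1. Report infection and asymptomatic infection by RT-PCR alone in the full set.
2. Report the serology-inclusive composite in participants assigned to a cohort with scheduled post-baseline nucleocapsid testing: Part 2 Cohorts A to C, and E if nucleocapsid is tested there. End follow-up for this composite at the last nucleocapsid result within the efficacy period, and count only events of either kind up to then.
3. Keep the existing full-set composite if wanted, labelled as having partial serology coverage, with the number of children tested in each arm.

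Cost: SAP wording and extra tables, with no new data. The composite would rest on about 552 children per age group, of whom about 138 are on placebo, so its interval widens. Cohorts A to C enrolled first and may differ from Cohort D in calendar exposure; Cohort E comes from selected sites. Cohort A adds only about two weeks after dose 2 (Day 43 to Day 57). Some Day 394 draws in Cohort C may fall after unblinding, which ends the blinded efficacy period under section 6.1. For these reasons the subset result should stand beside the full-set RT-PCR rate and not replace it.

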#### **6.4.2. Primary Analysis of Antibody-Mediated Immunogenicity Endpoints**

If an accepted serum Antibody (Ab) threshold of protection against COVID-19 is available based on data from other mRNA-1273 studies or external data, the number and percentage of participants with Ab greater than or equal to the threshold at Day 57 will be provided with a 2-sided 95% CI using the Clopper-Pearson method. If the lower bound of the 95% CI on the mRNA-1273 group is > 70%, the primary immunogenicity objective of this study will be considered to be met for that age group.

The number and percentage of participants with serum Ab greater than or equal to the threshold with 2-sided 95% CI will be provided by age and vaccination group as defined in [Section 6.1](#) at each post baseline time point. The CI will be calculated using the Clopper-Pearson method.

If an accepted serum Ab threshold of protection against COVID-19 is not established, immune response as measured by GM value and seroresponse rate in each age group based on Day 57 Ab levels will be compared with that in young adults ( $\geq 18$  to 25 years of age) using data from Study P301. An analysis of covariance model will be carried out with Ab at Day 57 as dependent variable and a group variable (a pediatric age group in Study P204 versus young adults [ $\geq 18$  to 25 years of age] in Study P301) as the fixed variable for each pediatric age group. The GM values of the pediatric age group at Day 57 will be estimated by the geometric least square mean (GLSM) from the model. The GMR (ratio of GM values) will be estimated by the ratio of GLSM from the model. The corresponding 2-sided 95% CI

will be provided to assess the difference in immune response between the pediatric age group (Study P204) compared to the young adults ( $\geq 18$  to 25 years of age) in Study P301 at Day 57. For each pediatric age group, the noninferiority of GM value will be considered demonstrated if the lower bound of the 95% CI of the GMR is  $> 0.667$  based on the noninferiority margin of 1.5 and the GMR point estimate  $\geq 0.8$  (minimum threshold). In addition, GMR with 95% CI calculated using t-distribution will be provided to assess if the two methods are consistent in the analysis results.

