## 6.5. Efficacy Analysis

Efficacy analyses will be performed using the FAS, mITT, mITT1 and PP Set for Efficacy. The mITT1 Set will be the primary analysis set used for efficacy analysis of efficacy endpoints starting from 14 days after first dose, and PP Set for Efficacy will be the primary analysis set used in the efficacy analyses for efficacy endpoints starting 14 days after second dose, unless otherwise specified. Subjects will be included in the treatment group to which they were randomized.

**Baseline SARS-CoV-2 status** is described in [Section 6.1](#). Baseline SARS-CoV-2 status, the serology test results at baseline, the RT-PCR test results at baseline will be summarized by age group and treatment group.

Participants with baseline positive or missing SARS-CoV-2 status will be excluded from the PP Set for Efficacy Analysis.

In this study, the serology test results and the RT-PCR test results will be summarized by visit.

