### **6.5.3 Sensitivity and Subgroup Analysis**

Sensitivity analysis for these efficacy endpoints will be performed with the same methods described above based on the FAS, mITT Set and mITT1 Set, with cases counted starting from date of first injection in Part 1 and starting from randomization in Part 2. A sensitivity analysis will be performed to include subjects with positive SARS-CoV-2 status at baseline.

In addition to the secondary efficacy endpoint COVID-19 (both CDC definition and P301 case definition) based on eligible symptoms and confirmed positive RT-PCR results (central lab or local diagnostic test) originally defined in section 6.5.1.3 and 6.5.1.4, a second set of COVID-19 (CDC definition and P301 case definition), considering both RT-PCR results and other non-RT-PCR test results including home antigen tests will also be derived, which may be considered as a sensitivity analysis of COVID-19 cases. For 6 to <12 years of age, the non-RT-PCR tests will be identified for associated sample collection dates on or after 01 Dec 2021 when home antigen tests started to become widely available, to be included in a sensitivity analysis of COVID-19 cases in the CSR. For 6 months to <2 years and 2 to <6 years of age groups, the non-RT-PCR tests will be identified in the entire study period for the sensitivity analysis for the EUA and CSR.

Subgroup analysis in Part 1 is not needed and it may be done for Part 2 (or Part 1 +Part 2).

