#### **6.5.1.3. Derivation of CDC Case Definition of COVID-19**

This is a secondary efficacy endpoint: the incidence of CDC Case Definition of COVID-19 starting 14 days after the second dose of mRNA-1273 in Part 2 open-label phase, and cases counted starting 14 days after the booster dose of mRNA 1273 in booster dose analysis. COVID-19 is defined as symptomatic disease based on the criteria specified in table listed below. Cases are defined as participants meeting clinical criteria based on both symptoms for COVID-19 and positive RT-PCR test results.

While Part 2 is still blinded for any age group, surveillance for COVID-19 symptoms will be conducted via biweekly telephone calls or eDiary. Subjects reporting CDC Case Definition of COVID-19 symptoms, as defined in Section 7.3.2 of the protocol, will be arranged an illness visit to collect a nasal swab for SARS-CoV-2.

Once the trial is unblinded for all age groups and thus no placebo comparator group is available going forward, COVID-19 surveillance will be discontinued, and COVID-19 cases will be reported under standard AE reporting per SoA only.

For this efficacy endpoint, a CDC Case Definition of COVID-19 case will be identified as a positive post-baseline RT-PCR test result, together with eligible symptoms, i.e. a positive PCR result of the eligible symptoms summarized below.

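### For the four secondary efficacy endpoints in blinded Part 2, the SAP prespecifies per-arm incidence rates only, with no mRNA-1273 versus placebo estimate or interval

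*SAP*

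**What the plan says.** The points below come from the SAP for the Part 1 open-label and Part 2 blinded phases unless noted.

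- **Allocation (4.3).** Within each age group, children "will be randomized in a 3:1 ratio to the mRNA-1273 arm" or placebo, up to 3,000 and 1,000.
- **Grouping (6.5).** "Subjects will be included in the treatment group to which they were randomized". The efficacy analysis period in 6.1 closes at unblinding.
- **Method (6.5.2).** There are two summaries. The first is a count: "The number and percentage of subjects who had an event (i.e. the first asymptomatic SARS-CoV-2 infection) will be summarized in the PP set for Efficacy". Next comes a rate for each arm: "The incidence rate will be provided by age and vaccination group, calculated as the number of cases divided by the total person-time". Its precision is given arm by arm: "The 95% CI of the incidence rate will be calculated using the exact method (Poisson distribution) and adjusted by person-time".
- **Sensitivity analyses (6.5.3).** "Sensitivity analysis for these efficacy endpoints will be performed with the same methods described above", on other analysis sets.
- **Primary immunogenicity model (6.4.2).** This contrast does not involve placebo. It uses "a group variable (a pediatric age group in Study P204 versus young adults" from Study P301.
- **Role of placebo (6.5.1.3 of the companion SAP for the open-label, booster and Part 3 phases).** "Once the trial is unblinded for all age groups and thus no placebo comparator group is available going forward, COVID-19 surveillance will be discontinued".

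**The concern.** Blinded Part 2 has what a randomised comparison of infection and disease needs: concurrent placebo, observer blinding, analysis as randomised and follow-up that stops at unblinding. The companion SAP ends surveillance because the placebo comparator is gone, so the sponsor sees placebo as a comparator. Yet the method section goes no further than describing each arm.

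Where this SAP wants a contrast, it names the estimator and the interval: a geometric mean ratio from the covariance model, and a Miettinen-Nurminen interval for the seroresponse difference. For the four efficacy endpoints it names neither.

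Anyone reading these tables will want to know how much lower the rate is on vaccine and how precisely that is known. Two one-sample intervals do not answer the second part. If VE is added later, the choice of ratio, interval method, analysis set, counting start and test basis (RT-PCR alone or with antigen tests) will be made with the results in view. Section 6.5 does name a main analysis set for each counting start, but nothing says which combination a VE figure would be taken from.

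**Working it through.** **Step 1: search for a contrast.** The efficacy sections of both SAPs (6.5 to 6.5.3 in each) were read for a ratio, difference, hazard model, test or definition of VE between mRNA-1273 and placebo. There is none. Times to event from randomisation are derived for infection, asymptomatic infection and CDC-defined COVID-19, but no stated analysis uses them. The companion SAP's 6.5.2 is also single-group incidence. The plan gives no VE, attack rate, alpha or power for these endpoints, so there is no stated figure to reproduce.

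**Step 2: what per-arm intervals can hide.** Assumed inputs: 48 vaccine and 28 placebo cases, 3,000 and 1,000 children (the ceilings in 4.3), equal follow-up.

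- Exact Poisson limits for x cases in T: lower = χ²(0.025; 2x)/(2T), upper = χ²(0.975; 2x+2)/(2T).
- Vaccine: 48/3,000 = 16.0 per 1,000 (11.8 to 21.2). Placebo: 28/1,000 = 28.0 per 1,000 (18.6 to 40.5). The intervals overlap.
- VE = 1 − 16.0/28.0 = 43%.
- Given 76 cases in total, vaccine cases are binomial with probability π, and the rate ratio is R = π/[3(1 − π)]. The Clopper-Pearson interval for 48/76 is 0.513 to 0.739, so R runs from 0.351 to 0.946 and VE from 5% to 65%.

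A second assumed case: 30 and 20 cases in 750 and 250 person-years give 40.0 (27.0 to 57.1) and 80.0 (48.9 to 123.6) per 1,000 person-years. These overlap, yet VE is 50% (7.1% to 72.5%).

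**Step 3: how large the difference could be.** Case counts were taken as independent Poisson with means 3,000 × AR × (1 − VE) and 1,000 × AR, where AR is the placebo attack rate. Each cell gives the chance, in percent, that the per-arm intervals separate in favour of vaccine, then the chance that the lower exact conditional 95% limit for VE exceeds 0.

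| True VE | AR 1% | AR 2% | AR 3% | AR 5% |
|---|---|---|---|---|
| 40% | 6 / 19 | 15 / 38 | 27 / 54 | 51 / 77 |
| 50% | 11 / 31 | 30 / 58 | 51 / 77 | 80 / 94 |
| 60% | 21 / 46 | 52 / 78 | 76 / 92 | 96 / 99 |
| 80% | 56 / 81 | 93 / 98 | 99 / 100 | 100 / 100 |

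The gap is largest, about 29 points, at VE 50% and AR 2%. It is essentially nil at VE 80% with AR 3% or more. With 2,250:750 children (25% loss assumed) and VE 50%, the pairs are 7/23, 20/45, 35/64 and 64/86. With no true effect, the one-sided error is 0.2% to 0.3% for the overlap reading and 1.6% to 2.1% for the direct contrast (nominal 2.5%).

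**The case against.** The best defence is that the plan does what its objectives ask. The secondary objectives in 2.2 are to evaluate incidence after vaccine or placebo, the endpoints in 3.2 are incidences, and Part 2 is sized in 4.2 for a safety database. Efficacy is meant to be inferred from antibody responses. On that reading 6.5.2 contradicts nothing. This stands, and it limits the weight of the point: the gap lies in a descriptive secondary analysis. It does not remove the point, because a descriptive aim is still better served by an interval on the contrast.

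A reader might go further and infer any of three things the documents do not support.

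- **That the trial can give no VE estimate.** Cases, person-time and rates are reported for both arms, so 1 minus the rate ratio follows directly. What is missing is the prespecification.
- **That placebo has no other use as a control.** It is a named group in the blinded-phase safety analyses (6.1), and adverse events and solicited reactions are tabulated by vaccination group (6.3). Those tables are side by side too, so this is the SAP's general style.
- **That efficacy will be judged by whether the intervals overlap.** The SAP states no such rule.

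The protocol is not at hand and might define VE. The SAP's clause that it prevails applies where methods differ, and silence is not a difference. Still, the method of comparing arms is ordinary SAP content, and this SAP is where a programmer would look for it.

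**Conclusion.** The point holds as a gap in prespecification for the four secondary efficacy endpoints of blinded Part 2, including their sensitivity analyses. It does not touch the immunobridging test or the safety analyses. It is worth correcting because the change is cheap, but the primary conclusions do not depend on it.

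The absence of a prespecified contrast rests on the text alone. The figures are illustrative: case counts, attack rates, VE and equal follow-up are all assumed. The loss of about 0 to 29 percentage points applies at 3,000:1,000 over VE 40% to 80% and placebo attack rates of 1% to 5%, and only for a reader who uses non-overlap as the criterion.

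**What to change.** Add to 6.5.2, for each age group in the Part 2 blinded phase and each of the four efficacy endpoints:

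- mRNA-1273 and placebo are compared as randomised, with VE = 1 − (mRNA-1273 incidence rate / placebo incidence rate).
- The two-sided 95% CI comes from the exact method conditional on the total number of cases, adjusted for person-time.
- The PP Set for Efficacy is used when counting from 14 days after Dose 2, and the mITT1 Set when counting from 14 days after Dose 1.
- Person-time for this contrast starts at the same point as case counting. At present 6.5.2 starts it at randomisation while cases count from 14 days after a dose, and VE should not inherit that mismatch.
- The same contrast is repeated in the 6.5.3 sets.
- The result is labelled descriptive secondary estimation outside the alpha-controlled sequence, and the per-arm rates are kept.

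The cost is a paragraph of text, extra columns in tables already planned and a realigned person-time derivation. No new data, participants or alpha are needed. The drawback is wide intervals where cases are few: with an assumed 15 versus 10 cases at 3:1 person-time, VE is 50% with 95% CI −24.5% to 79.0%.
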